1. STATISTICAL METHODS PLANNED IN THE PROTOCOL AND DETERMINATION OF SAMPLE SIZE

The objective of this analysis plan is to describe the planned full study analysis.

1.1. Statistical and Analytical Plans

1.1.1. Definitions and General Considerations for Data Analysis

1. All calculations will be performed in a GCP-compliant environment using SAS statistical software, version 9.2 or later, StatXact, version 10 or later or OR-DBM MRMC (2.5) or later.
2. This Statistical Analysis Plan (SAP) is based on Clinical Trial Protocol Imagio Feasibility MRMC Study of Optoacoustic Images vs. Imagio Ultrasound to Guide Decision to Biopsy, September 24/November 1, 2018 – Version 3.0.
3. This study is a single arm, controlled, blinded, multi-reader, multi-case (MRMC) study using a sequential design.
4. This feasibility study will be registered at clinicaltrials.gov.
5. There will be up to 12 independent readers to evaluate images using standardized equipment at American College of Radiology (ACR).
6. All readers will read all images utilizing (IUS) and before (IUS+OA pre) and after the SenoGram (SG) prompt (IUS+OA post); prior to all image reads, all readers will have access to mammography images and a clinical history as collected in PIONEER.
7. A total of 155 complete read sets from the original PIONEER Intention-to-Diagnose (ITD) population will be randomly selected from within the PIONEER Study. Only once mass is to be selected per PIONEER subject.
 - Cohort 1 will consist of 75 benign and 45 malignant masses classified by CDU as BI-RADS 3 to 5 selected at random in proportion to the original distribution of Bi-RADS classifications among subjects in the PIONEER Study. To facilitate the alignment of the PIONEER Pivotal Study data with the Feasibility Study data, the mass image set sampling plan will select a proportion with and without mammograms for benign masses. [Note: mammograms were present for nearly all malignant masses.]
 - Cohort 2 will consist of 30 malignant masses with at least one false negative read from the PIONEER study to assess if the excess FN rate observed with OA in the PIONEER study can be reversed. The same proportional sampling strategy with respect to CDU Bi-RADS will be used. Cohort 3 will consist of five DCIS, lymphoma, or phyllodes masses; this will assess if these atypical cases do not introduce FNs or FPs. [Note: Due to the small size, Cohort 3 results will be listed only and not be summarized.]
8. Cohort data will not be combined across cohorts.

9. To assess intermediate performance an interim analysis is planned after each reader has completed at least 72 Cohort 1 masses.
10. The primary endpoint is to evaluate the gain in specificity at fixed sensitivity for IUS+OA post vs IUS; IUS+OA pre-will be compared to IUS and IUS+OA post.
11. There are no formal hypothesis tests for this Feasibility Study; this study will be used to inform Seno on the design and sample size of a subsequent pivotal study.
12. Feasibility Study data will not be used for registration purposes.
13. Feasibility Study data will not be combined with the subsequent pivotal study but will be used to determine effect sizes to power the subsequent pivotal study.

1.1.2. Classification of Cancer Status

Feasibility Study masses will be classified as biopsy-confirmed cancer, biopsy-confirmed benign or Truth Panel benign from PIONEER.

1.1.3. Analysis Populations

Safety results for the safety population were reported for the entire sampling frame for this Feasibility Study in the PIONEER CSR. There will be no safety reporting for this study.

Masses will be selected according to the SENO Sampling Plan (11SEP2018).

There will be three cohorts as described above:

1. Cohort 1: PIONEER Feasibility Simple Random Sample
2. Cohort 2: PIONEER False Negatives (FN)
3. Cohort 3: PIONEER DCIS, lymphoma or phyllodes tumors

At study completion the number and type of protocol deviations (PD) will be reviewed to determine whether there are missing or incomplete reads that would impact analyses. Significant findings will report findings to the study sponsor and used to improve the pivotal study design.

1.1.4. Disposition of Masses

A total of 155 masses were selected from the PIONEER ITD population; 120 masses for Cohort 1, 30 for Cohort 2, and 5 for Cohort 3. A 10% over-sampling allowed for replacement of any mass that might prove unreadable for Feasibility. Replacement of any masses will be documented in the CSR.

1.1.5. Demographic and Other Baseline Characteristics

Clinical presentation and medical history (from the PIONEER database) of site-determined CDU Bi-RAD score, referral indication, palpability of mass, breast density, age, menopausal status, presence of breast implants, number of masses (in PIONEER), and mammographic intent will be summarized using descriptive statistics. Mass size and depth, as recorded by the feasibility readers, will be summarized using descriptive statistics.

Summary tables will display demographic and baseline characteristics by cohort and by diagnostic status (benign+TPB, cancer). Cohorts will not be combined for any displays or analyses.

1.1.6. Medical History and Concomitant Medications

Detailed medical history (as presented to the readers) will be listed. Concomitant medications are irrelevant to this study.

1.1.7. Effectiveness Analysis

There are no formal tests of hypotheses for this study. P-values that are generated will be regarded as descriptive statistics. IUS+OA pre-is OA before the SenoGram; IUS+OA post is the reader input OA after viewing the SenoGram. The following will be used to assess feasibility of a pivotal study.

Table 1: Effectiveness Analysis for Study Endpoints

Endpoints by Cohort	Analysis/Software
Cohort 1: Primary	

Gain in specificity IUS+OA post vs. IUS at fixed sensitivity (95-99%) interpolated from the ROC AUC curves. This analysis will be repeated for IUS+OA pre vs. IUS and IUS+OA post vs. IUS+OA pre.
 
A recommended pivotal study sample size will be determined using multiple sources, including OR-DBM MRMC sample size program.
 
Review of entire feasibility study report will be used to recommend efficacy endpoints for the pivotal study.
	
OR-DBM MRMC
 
Sample Size: OR-DBM-MRMC Power program, nQuery v7, SAS (PROC POWER), and/or PASS v15.05.

Cohort 1: Secondary	

Partial AUC: Difference (IUS+OA post vs. IUS) in partial ROC AUC curves for 95-99% sensitivity. This analysis will be repeated for IUS+OA pre vs. IUS and IUS+OA post vs. IUS+OA pre.
	
OR-DBM MRMC & methods as per McClish

Specificity and Sensitivity: Observed and model-adjusted specificity and sensitivity will be reported for IUS+OA post vs. IUS using a 2% POM cutoff.
 
These analyses will be repeated for
	
SAS PROC GEE and MIXED treating readers as independent observations and readers as correlated and then readers correlated and masses as independent.

IUS+OA pre vs IUS and IUS+OA post vs IUS+OA pre, and for POM cutoffs of 1%, 3%, 4%, and 5%.
	
Two-sided 95% confidence intervals for sensitivity and specificity will be computed for IUS, IUS+OA pre, the IUS+OA post, and the 3 pairwise differences.

Negative Likelihood Ratios (NLR) for IUS and IUS+OA post, NLR defined as $((1 - \text{observed sensitivity}) / \text{observed specificity})$
	
SAS: Univariate 95% CI for PLR and NLR with variances fit using the logarithmic transformation and the delta method, reference PIONEER Table 14.2.3.2.


BI-RADS (BR): Downgrade (IUS+OA post) defined as:
 
 • IUS in BR 4a and IUS+OA post in BR 2-3 or • IUS in BR 3 and IUS+OA post in BR 2 
BI-RADS: Upgrade defined as:
 
 • IUS in BR 2 and IUS+OA post in BR 3-5 or • IUS in BR 3 and IUS+OA post in BR 4-5 
Tables will be repeated for IUS x IUS+OA post, IUS vs IUS+OA pre and IUS+OA pre vs IUS+OA post.
	
SAS: BI-RADS Grade Changes (Grouped BI-RADS), simple counts with 95% CI.
 
Benign+TPB: Reference PIONEER Table 14.2.13.4 [t_14_02_13_birch1_04]
 
Cancers: Reference PIONEER Table 14.2.13.7 [t_14_02_13_birch2_07]
 
Note: change from 99% CI to 95% CI

Net grade change – All masses – weight (W) that results in a significant OA+IUS vs IUS reflecting the FP advantage minus the weighted FN disadvantage.
	
SAS: PROC GENMOD and MIXED linear models will contrast difference in FN and FP to demonstrate clinical benefit.
 
Tables to be repeated for IUS x IUS+OA post, IUS vs IUS+OA pre and IUS+OA pre vs IUS+OA post

SenoGram performance using the following metrics from the study endpoints:
 
a) Sensitivity and specificity for SenoGram classification based on predicted probability and the SenoGram threshold, with separate analysis for each study cohort and with subgroup analysis for masses with and without mammogram BI-RADS data.
	
For each metric, a summary table for each reader (where appropriate) and for all readers to contain the following:
 
 • Measured value using Reader-01 feature data. • Estimated value from SenoGram cross-validation with PIONEER feature data. • Estimated value from SenoGram predictions for cohort masses with


b) Specificity at fixed sensitivity (98%) for SenoGram classification as in (a).
 
c) Partial AUC (over sensitivity range 95% to 99%, inclusive, using the McClish normalization) for SenoGram classification as in (a).
 
d) Partial AUC (over sensitivity range 95% to 99%, inclusive, using the McClish normalization) for SenoGram classification as in (a).
 
e) Sensitivity and specificity for SenoGram classification based on prediction intervals and the SenoGram threshold. The prediction will be considered inconclusive if the SenoGram threshold lies within the prediction interval; otherwise the interval prediction is treated the same as a probability prediction. As in (a), each cohort will be analyzed separately, with subgroup analysis for masses with and without mammogram BI-RADS data.
 
f) Specificity at fixed sensitivity (98%) for SenoGram classification using the prediction interval as in (d).
 
Partial AUC (over sensitivity range 95% to 99%, inclusive, using the McClish normalization) for SenoGram classification using the prediction interval as in (d).
	
PIONEER data.

Cohort 1: Exploratory
	

OA Feature Score Distributions:
 
 • Benign vs. malignant masses • Benign masses only – mammogram vs no mammogram 
POM Score Distributions:
	
Summary Statistics by reader. Average over readers and then summarize means for overall. Use Wilcoxon for test statistic.
 
Reference PIONEER T14.2.10.1 [t_14_02_1x_feat-10-_01]

 Benign vs. malignant masses Benign masses only – mammogram vs no mammogram 	Reference PIONEER Table 14.2.9.1 [t_14_02_09_pom-01]
Cohort 2: Secondary	
Observed and model-adjusted sensitivity	SAS: PROC GEE and MIXED
BI-RADS: Up and downgrades (defined above) for cancers only	
SAS: BI-RADS Grade Changes (Grouped BI-RADS), simple counts with two-sided 95% CI.
 
Cancers: Reference PIONEER Table 14.2.13.7 [t_14_02_13_birch2_07]
 
Note: change from 99% CI to 95% CI
 
Tables to be repeated for IUS x IUS+OA post, IUS vs IUS+OA pre and IUS+OA pre vs IUS+OA post

Cohort 3: Listings Only	

All Cohorts (Combined)
 
Summary statistics to describe the SenoGram usage [n(%)] by individual reader and overall. Summary statistics for the SenoGram effect on reader confidence.
	SAS: Proc Freq & Proc univariate

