## 2.2 Secondary Endpoints

To evaluate the following overall and for individual readers for:

1. the partial ROC AUC corresponding to 95-99% sensitivity with specificities extrapolated from the respective Imagio and IUS ROC curves as applicable.
  - the observed and model-adjusted specificity and sensitivity
  - the Negative Likelihood Ratio (NLR) defined as  $((1-\text{sensitivity})/\text{specificity})$
  - the upgrade and downgrade metrics:
    - the percent correct of downgrades for benign masses from IUS BI-RADS 4a to Imagio (IUS+OA) BI-RADS 2-3, and from IUS BI-RADS 3 to Imagio (IUS+OA) BI-RADS 2
    - the percent incorrect of upgrades for benign masses from IUS BI-RADS 2-3 to Imagio (IUS+OA) BI-RADS 4-5 and from IUS BI-RADS 2 to Imagio (IUS+OA) BI-RADS 3-4-5
    - the percent of incorrect downgrades for malignant masses from IUS BI-RADS 4-5 to Imagio (IUS+OA) BI-RADS 2-3; and
    - the percent of correct upgrades for malignant masses from IUS BI-RADS 2-3 to Imagio (IUS+OA) BI-RADS 4-5.
2. the Cumulative effect of downgrades and upgrades for combined benign masses and malignant masses.
3. the SenoGram usage:
  - Utilization percent reported by the readers
  - Sensitivity and specificity discordance with Imagio (IUS+OA) Downgrades and upgrades versus Imagio (IUS+OA) and IUS, separately for benign and malignant masses
  - POM paired differences versus Imagio (IUS+OA) and IUS, separately for benign and malignant masses.
4. the SenoGram performance:
  - Sensitivity and specificity compared to sensitivity and specificity estimated from cross-validation and hold-out validation.
  - Partial AUC for individual users and overall corresponding to 95-99% sensitivity
  - Separate assessment of Senogram performance with and without mammographic data input.

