### 4. STUDY DESIGN

This will be a single arm, controlled, blinded, multi-reader, multi-case (MRMC) study using a sequential design. The study will include 5-12 readers depending on qualifications and availability.

Imagio (IUS+OA) Training to be completed prior to any reads taking place. Read 1 is immediately followed by Read 2 within the same read session.

- Read 1 (Control): Mammogram (if available) + History + IUS (stills and videos provided), IUS Probability of Malignancy (POM) and BI-RADS scored and the data form locked.
- Read 2 (Test): Mammogram (if available) + History + IUS (stills and videos provided), and Imagio (IUS+OA) (stills and videos provided). An interim IUS POM and BI-RADS is recorded as well as a combined Imagio (IUS+OA) POM and BI-RADS Pre and Post SenoGram on separate data forms.

Read 1 reflects the information available to a radiologist when evaluating standard ultrasound images, taking under consideration the mass and patient history and assessing mammogram results as available. The History details to be provided are summarized under the Blinding section of the protocol. Read 1 (IUS reads) will serve as the control representing current clinical practice. Read 2 (IUS+OA) will be considered the test read and reflect a pre SenoGram IUS and Imagio (IUS+OA) POM and BI-RADS assessment in addition to a post SenoGram IUS and Imagio (IUS +OA) POM and BI-RADS assessment. Following the display of the SenoGram within the Post SenoGram data form, the IUS and OA feature scores are locked, and the reader is prompted to provide a Post SenoGram POM and BI-RADS. Once the Post SenoGram POM and BI-RADS are provided, the form is locked.

A total of 155 complete read sets from the original PIONEER Intention-to Diagnose (ITD) population will be randomly selected from within the PIONEER Study.

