### 4. NLR

The NLR  $((1-\text{sensitivity})/\text{specificity})$  will be computed using the standard formula with two-sided 95% CIs computed using exact 2x2 contingency table methods. A two-sided 95% CI for the NLR  $<1$  and favoring OA will indicate improvement in NLR; the relative NLR will also be computed relative to IUS. The same analysis will be performed for SenoGram versus IUS and versus Imagio (IUS+OA).

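### The SAP swaps the protocol's exact NLR intervals for log/delta ones that do not exist at zero false negatives, omits the relative NLR, and does not declare the change

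*SAP*

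**What the plan says.** Protocol 2.2 makes the NLR, (1 − sensitivity)/specificity, a secondary endpoint. Its opening line, "To evaluate the following overall and for individual readers for", asks for results at both the pooled and the reader level.

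Protocol 9.8 item 4 plans the NLR "with two-sided 95% CIs computed using exact 2x2 contingency table methods". It says that an interval below 1 and "favoring OA will indicate improvement in NLR", and it adds a relative NLR against IUS. It also asks for the same analysis for the SenoGram.

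SAP 1.1.7 Table 1 has one row on this endpoint: "Negative Likelihood Ratios (NLR) for IUS and IUS+OA post", defined from observed sensitivity and observed specificity. The method given is "Univariate 95% CI for PLR and NLR with variances fit using the logarithmic transformation and the delta method", with a PIONEER table cited as reference. The row has no ratio or other contrast of the two NLRs, no continuity correction, and no exact fallback. SAP 1.1.7.1.2 rules out imputation of missing data but does not deal with zero counts.

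SAP Section 2, which records changes to the planned analyses, mentions only the mammogram sampling.

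**The concern.** Three things changed between two current documents without being declared. The interval method moved from exact to asymptotic, the comparison with IUS on this measure disappeared, and nothing records either step.

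The method matters because the NLR has the false-negative rate as its numerator. At high sensitivity that count is small and may be zero, which is where the log transformation breaks down. A reader who misses no cancer would have a point estimate of 0 and no interval, so could not be assessed by the protocol's own reading of the NLR.

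The missing contrast matters because the secondary objective in Protocol 1.2 is the NLR of IUS versus Imagio. Separate intervals for each modality show whether each is informative, but not whether one improves on the other. SAP Table 1 uses the review of the whole report to recommend pivotal endpoints, so an incomplete NLR output feeds into that choice.

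**Working it through.** **Inputs.** Cohort 1: "Cohort 1 will consist of 75 benign and 45 malignant masses" (SAP 1.1.1). Readers: "The study will include 5-12 readers depending on qualifications and availability" (Protocol 4), so 5 to 12. The documents give no NLR precision figure to reproduce, and no expected sensitivity or specificity at the POM cutoff. The values used below for both are assumptions.

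**1. Where the interval fails.** For one reader with FN missed cancers of 45 and TN correctly negative benign masses of 75:

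NLR = (FN/45)/(TN/75)

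SE of ln NLR = √(1/FN − 1/45 + 1/TN − 1/75)

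Interval = exp(ln NLR ± 1.96 × SE)

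At FN = 0, both ln NLR and 1/FN are undefined.

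**2. How often, per reader and modality.** P(FN = 0) = s^45 for true sensitivity s at the cutoff. The expected number of readers affected is that probability times 5 or 12.

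| s | P(FN = 0) | Expected, 5 readers | Expected, 12 readers |
|---|---|---|---|
| 90% | 0.9% | 0.04 | 0.10 |
| 95% | 9.9% | 0.5 | 1.2 |
| 97% | 25.4% | 1.3 | 3.0 |
| 98% | 40.3% | 2.0 | 4.8 |
| 99% | 63.6% | 3.2 | 7.6 |

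The expected counts do not require readers to be independent.

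**3. Pooled over readers.** With 45 × 5 = 225 or 45 × 12 = 540 malignant reads treated as independent, P(FN = 0) at 98% is 0.98^225 = 1.1% or 0.98^540 < 0.01%. At 99% it is 10% or 0.4%. All readers read the same cancers, so positive correlation would raise these figures, but never above the per-reader figure.

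**4. Small subgroups.** SAP 1.1.7.1.1 reruns primary and secondary endpoints with and without mammograms (SAP 1.1.7.1.5 mentions benign masses only). SAP Section 2 puts missing mammograms at about 3% of malignant masses: 0.03 × 45 = 1.35, or one or two cancers. Per reader, P(FN = 0) then runs from 0.95² = 90% to 0.99¹ = 99% for sensitivity of 95–99%. Pooled at 98%, with 5 reads (one cancer, 5 readers) to 24 reads (two cancers, 12 readers), it is 0.98^5 = 90% to 0.98^24 = 62%.

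**5. Coverage where the interval exists.** Enumerating Binomial(45) × Binomial(75) outcomes with specificity assumed at 30–50%, coverage given FN > 0 is about 96% at 95% sensitivity, 91–93% at 98% and 82–85% at 99%.

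**6. Why the zero rule must be named.** Take FN = 0/45 and TN = 30/75 (specificity 40%, assumed). The log/delta interval does not exist. The exact 95% upper limit for the false-negative rate is 1 − 0.025^(1/45) = 7.9%. A score interval for the ratio gives an NLR upper limit of about 0.20. Adding 0.5 to each cell gives NLR (0.5/46)/(30.5/76) = 0.027, interval 0.0017 to 0.43. Two reasonable rules thus differ more than twofold in the upper limit.

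**7. The relative NLR has its own zero problem.** NLR(Imagio)/NLR(IUS) is undefined when IUS has FN = 0. A plain bootstrap does not avoid this at reader level. If a reader misses one of 45 cancers on IUS, (44/45)^45 = 36% of resamples contain no miss; with two missed, (43/45)^45 = 13%.

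**The case against.** Several points limit this concern, and most of them stand.

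- **Frequency.** A reader might take the 95–99% range and the 98% target as the sensitivity at which the NLR will be computed, and conclude that missing intervals will be common. The documents do not support that. Those figures belong to the endpoints interpolated from the ROC curve. The NLR uses observed sensitivity, presumably at the 2% POM cutoff, although the NLR row does not restate it. Protocol 4 refers to an excess false-negative rate with OA in PIONEER, which gives no reason to assume 98%. At 90% the problem is rare.
- **Who is affected.** It is tempting to say that the best readers lose their interval. FN = 0 means only 100% observed sensitivity, which a reader can also reach by scoring nearly every mass above the cutoff, at very low specificity.
- **Level.** The SAP row does not say that the NLR is by reader; that requirement comes from Protocol 2.2. In the full Cohort 1 the pooled NLR would seldom fail.
- **The PIONEER table.** The cited table is not available and may contain a zero-count rule. Failure is established for the method as the SAP states it, not for the eventual program.
- **The below-1 criterion.** One might infer that the protocol judges improvement on NLR below 1 alone. It does not: it also requires the result to favour OA and adds the relative NLR.
- **The comparison.** The SAP's omission is silence, not an explicit withdrawal. SAP Table 1 does give intervals for the paired differences in sensitivity and specificity, which are the NLR's two components. Only the contrast of the NLRs themselves is missing.
- **Consequence.** The study tests no formal hypotheses, and the NLR is not among the illustrative move-forward criteria. However, Protocol 9.1 bases the decision on primary and secondary endpoints collectively, so the effect is not nil.

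None of this reconciles the two interval methods, supplies a zero-count rule, or restores the relative NLR.

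**Conclusion.** The concern holds in a limited form. The protocol and SAP specify different interval methods for the NLR, the SAP leaves out the relative NLR, and neither change is declared. The SAP's stated method gives no interval at FN = 0.

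The size depends on an operating point that the documents do not give: per reader and modality, from 0.9% at 90% sensitivity through 10% at 95% and 40% at 98% to 64% at 99%. The effect falls on the reader-level NLRs that Protocol 2.2 requires and on small subgroups. It seldom reaches the NLR pooled over readers in the full cohort. The pooled figures assume independent reads, and the coverage and zero-rule examples assume specificity of 30–50% and 40% respectively.

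This is a secondary, descriptive endpoint and no formal test is at risk. The point should still be settled before analysis, because reasonable zero-count rules give materially different upper limits.

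**What to change.** In SAP 1.1.7 Table 1, NLR row:

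1. For reader-level and subgroup NLRs, restore the protocol's exact method, or name a score interval that remains valid at zero counts. State the POM cutoff and that results are by reader and overall.
2. Reinstate the relative NLR, Imagio versus IUS, pooled over readers. Its interval should account for the pairing of modalities on the same masses and for several readers reading each mass.
3. At reader level, pre-specify a zero-valid approach to the relative NLR, or state that the paired sensitivity and specificity differences are reported instead when IUS has FN = 0. A plain bootstrap of the ratio is not enough.
4. State that improvement over IUS is judged on the relative measure.
5. List the change in SAP Section 2. If the cited PIONEER table contains a zero-count rule that is to be kept, write it into the SAP.

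The cost is SAP wording and minor programming, with no new reads. The intervals may be somewhat wider where an exact method is used.

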### 1.2 Secondary Objectives

To evaluate the following overall and for individual readers for IUS versus Imagio (OA+IUS):

- the Imagio (IUS+OA) partial Receiver Operator Characteristic (ROC) Area under the Curve (AUC) for 95-99% vs IUS for 95-99% sensitivity
- the sensitivity and specificity for Imagio (IUS+OA) versus IUS according to multiple models for readers and masses used for assessing sources of variation
- the Negative Likelihood Ratio (NLR) for IUS versus Imagio (IUS+OA).
- the Imagio (IUS+OA) downgrades and upgrades relative to IUS, separately, for benign and malignant masses
- the net gain (new True Positives [TP] + new True Negatives [TN] – new False Positives [FP] – new False Negatives [FN]) estimate of Imagio (IUS+OA) versus IUS combining benign and malignant masses
- the usage and performance of the SenoGram model for the purposes of determining whether it will be adjusted prior to starting the pivotal study

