1.1.7.1. Feasibility Analysis Methodology

Data Analyses

Hypotheses generating analyses will be based on independent readers for POM, BI-RADS and feature scores (IUS, IUS+OA pre, IUS+OA post) individually and overall. There are no formal hypothesis tests; p-values from all analyses are descriptive only. There are no adjustments for multiple testing. There will be no adjustment in p-values reported for the planned interim analysis after a minimum of 72 reads by each reader in Cohort 1. Truth (determination of malignant biopsy, benign biopsy, or TPB) will be taken from PIONEER.

The analyses below will be done for Cohort 1, repeated for malignant masses only for cohort 2. No summaries (listings only) will be done for the 5 masses in Cohort 3.

The specificity advantage of IUS+OA post vs IUS, IUS+OA pre vs IUS and IUS+OA post vs IUS+OA pre will be compared at fixed 98% sensitivity. The software package OR-DBM MRMC [Version 2.5 or later] will be used for this analysis of OA gain as interpolated from the ROC curves.

Specificity and sensitivity will be calculated by reader and overall for IUS, IUS+OA pre, IUS+OA post, and the 3 pairwise differences [PROC GENMOD, readers as independent,

repeated as masses as independent]. Specificity and sensitivity will be calculated (not model-adjusted) using the 2% POM cutoff for IUS+OA pre, IUS+OA post and IUS; and then for robustness analyses, for 1%, 3%, 4%, and 5% cutoffs.

Clinically relevant up and downgrades based on BI-RADs are defined as:

- Downgrades: IUS in BR 4a and IUS+OA post in BR 2-3 or IUS in BR 3 and IUS+OA post in BR 2
- Upgrades: IUS in BR 2 and IUS+OA post in BR 3-5 or IUS in BR 3 and IUS+OA post in BR 4-5.

These definitions likewise hold for differences for IUS vs IUS+OA pre and IUS+OA pre and IUS+OA post. These clinically relevant up and downgrades will be reported by reader and overall for benign and cancers separately. For benign masses, up and downgrades will be reported for masses with and without mammograms.

To assess the net effect of downgrades and upgrades, a net gain will be computed in SAS using contrast statements for the ANOVA to determine weight (W) of the malignant outcomes (TP and FN) to determine the value $(A-B+W(C-D))$ that achieves statistical significance, where A, B, C and D are defined as:

- A. Benign Masses correctly downgraded using IUS+OA post
- B. Benign Masses incorrectly upgraded using IUS+OA post
- C. Malignant masses correctly upgraded using IUS+OA post

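### The SAP's intervals for overall BI-RADS grade changes and NLR ignore that all readers score the same masses, and its NLR plan lacks a comparison with IUS and a rule for zero false negatives

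*SAP*

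**What the plan says.** **Grade changes.** SAP Table 1 gives "SAS: BI-RADS Grade Changes (Grouped BI-RADS), simple counts with 95% CI" for Cohort 1 and "SAS: BI-RADS Grade Changes (Grouped BI-RADS), simple counts with two-sided 95% CI" for Cohort 2. SAP 1.1.7.1 adds: "These clinically relevant up and downgrades will be reported by reader and overall for benign and cancers separately".

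**NLR.** The endpoint cell of SAP Table 1 reads "Negative Likelihood Ratios (NLR) for IUS and IUS+OA post", one value per modality. The method cell reads "SAS: Univariate 95% CI for PLR and NLR with variances fit using the logarithmic transformation and the delta method". Protocol 2.2 wants the secondary endpoints, NLR and grade changes included, both overall and for each reader.

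**Crossing.** SAP 1.1.1 item 6: "All readers will read all images utilizing (IUS) and before (IUS+OA pre) and after the SenoGram" prompt. Protocol section 4 allows 5 to 12 readers.

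**Other rows of SAP Table 1.** The primary endpoint and partial AUC use OR-DBM MRMC. Sensitivity and specificity use GEE and MIXED, and net grade change uses GENMOD and MIXED. Feature and POM scores have an explicit overall rule: "Average over readers and then summarize means for overall". The grade-change and NLR rows have none; they cite PIONEER tables that are not in the documents.

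**Protocol 9.8.** The opening text names Obuchowski-Rockette with readers and masses both random, alongside a model with masses fixed. It asks for 95% intervals on differences in upgrade and downgrade percentages. Item 4 (NLR) prescribes exact 2x2 intervals and a relative NLR against IUS, and takes an interval below 1 that favours OA as a sign of improvement. The SAP's grade-change and NLR rows carry over none of this, and the SAP's section on changes mentions only mammogram sampling.

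**The concern.** Twelve readers scoring 75 benign masses give 900 reads but only 75 independent masses. A simple-count or univariate interval computed on all reads treats the 900 as independent. The overall percentages and NLR would then look more precise than they are.

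The NLR plan has three further gaps that do not depend on pooling. The log/delta interval fails when a reader misses no cancer. The protocol and SAP name different interval methods. The protocol's secondary objective compares IUS with Imagio, but the SAP row provides no comparison, and the protocol's criterion sets the interval against 1 rather than against IUS.

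These results are descriptive. They still feed the collective move-forward judgement (Protocol 9.1) and the recommendation of pivotal endpoints (SAP Table 1), and benign downgrades are among the illustrative criteria in Protocol 9.8 item 3.

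**Working it through.** The documents state no interval width or correlation for these endpoints, so there is no plan figure to reproduce.

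**Inputs from the documents:** R = 5 to 12 readers; Cohort 1 has 75 benign and 45 malignant masses; intervals are 95% two-sided. **Assumed:** correlation ρ of the yes/no grade change between readers of the same mass, 0.1 to 0.5; no reader variance; benign downgrade rate 30%.

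**1. All reads in the denominator.** True SE / pooled SE = √(1+(R−1)ρ). Actual coverage = 2Φ(1.96/ratio) − 1.

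| R | ρ | Ratio | Coverage of nominal 95% |
|---|---|---|---|
| 5 | 0.1 | √1.4 = 1.18 | 90% |
| 5 | 0.5 | √3.0 = 1.73 | 74% |
| 12 | 0.1 | √2.1 = 1.45 | 82% |
| 12 | 0.5 | √6.5 = 2.55 | 56% |

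**2. Restricted denominators.** Protocol Table 2 divides by reads that were BR4a or BR3 on IUS, so fewer reads per mass count. Suppose half do.

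- Fixed half (R/2 reads per mass): √(1+1.5ρ) = 1.07-1.32 with 5 readers; √(1+5ρ) = 1.22-1.87 with 12.
- Binomial half: the effective number per mass is E[n²]/E[n] = 7.5/2.5 = 3 with 5 readers and 39/6 = 6.5 with 12. The ratios are √(1+2ρ) = 1.10-1.41 and √(1+5.5ρ) = 1.24-1.94.
- Taken together: 1.07-1.41 and 1.22-1.94.

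Half-widths for a 30% rate with a fixed half of the reads:

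- 5 readers: 1.96√(0.21/187.5) = 6.6 points; should be 6.6×1.07 to 6.6×1.32, about 7.0-8.7.
- 12 readers: 1.96√(0.21/450) = 4.2 points; should be about 5.2-7.9.

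**3. Overall NLR.** A 4,000-run probit simulation assumed sensitivity 96%, specificity 40%, and a mass variance of 0.2 to 0.4 on a latent scale of total variance 1. The pooled log/delta interval covered 94-90% with 5 readers and 89-79% with 12. Adding a reader variance of 0.05 at the upper mass variance lowered this to 86% and 75%. With no correlation, coverage was 95-96%.

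**4. Zero false negatives, one reader.** Var(log NLR) = Se/(45(1−Se)) + (1−Sp)/(75·Sp). At an observed Se of 1, the log and the first term are both undefined. The probability is Se^45: 0.95^45 = 0.10, 0.97^45 = 0.25, 0.98^45 = 0.40. With 12 readers, about 1, 3 and 5 of them would have no interval.

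**5. Comparing NLR with 1.** NLR is below 1 whenever sensitivity + specificity exceeds 1. Take IUS at 95%/45% and IUS+OA at 95%/40%. The NLRs are 0.05/0.45 = 0.11 and 0.05/0.40 = 0.125, so IUS+OA is worse. For one reader the log SE is √(0.95/2.25 + 0.60/30) = 0.665, and the upper limit for IUS+OA is 0.125·exp(1.96×0.665) = 0.46, well below 1. The interval part of the criterion says almost nothing about IUS. The comparison rests on the words about favouring OA, which have no stated interval.

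**The case against.** **Pooling is not stated.** A reader might infer that the SAP pools all reads as independent. It does not say so, and the cited PIONEER tables may define the overall interval. This stands: the narrowness is conditional, and the certain defect is that the only stated methods do not suit an overall result.

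**The protocol covers much of this.** It names Obuchowski-Rockette and the relative NLR, and the SAP withdraws neither. That makes the fault an incomplete carry-over. It does not resolve it, because the SAP rows name other methods.

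**The target of inference matters.** With masses fixed, as in one of the protocol's two models, and no reader variance, the true/pooled ratio is √(1−ρ) = 0.71-0.95, so pooled intervals would be too wide. This also stands. The inflation applies to inference beyond the sampled masses, which is what a pivotal study needs.

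**The largest figures are extreme.** Coverage of 56% needs 12 readers, ρ = 0.5 and every read counted. With half the reads, coverage is 93-83% (5 readers) and 89-69% (12).

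**Exact intervals may already handle zero cells.** They may, but the SAP replaces them with log/delta.

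**Readings that go too far.** Single-reader grade-change intervals are unaffected, since each mass counts once. Pivotal sizing is not directly affected, since SAP 1.1.7.1 uses an MRMC program. Nor should the protocol's NLR criterion be charged with passing about half of null studies: that follows largely from reading the favouring clause as a point estimate, and the sentence is ambiguous.

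**Conclusion.** The concern holds in conditional form and should be fixed. The SAP names no interval suited to overall grade changes or overall NLR. If its stated methods are applied to all reads, the intervals are too narrow for inference to new masses and readers. The size rests on an assumed ρ of 0.1-0.5 and on how many reads enter each denominator. Reader variance would add to it.

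The NLR defects need no pooling assumption: an interval that is undefined in 10-40% of single-reader tables at sensitivities of 95-98%, a conflict between protocol and SAP on the method, a missing relative NLR, and an improvement criterion whose interval is set against 1. Sensitivity and specificity differences do get model-based intervals, and NLR is not among the illustrative move-forward criteria, which limits the consequences.

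**What to change.** - Limit simple-count intervals to single-reader grade-change tables.
- For overall upgrade and downgrade percentages, their differences, and NLR, use the Obuchowski-Rockette reader-and-mass method already in Protocol 9.8, on the log scale for NLR. In simulation it covered 94-95% for grade changes with all reads counted and 91-96% for overall NLR.
- Reconcile Protocol 9.8 item 4 with the SAP NLR row on one single-reader interval that is defined with zero false negatives, exact or score. A score interval for 0/45 false negatives with 34/75 true negatives runs from 0 to 0.17.
- Add the relative NLR (IUS+OA divided by IUS), paired by mass, with a descriptive 95% interval.
- Base any statement that NLR improved over IUS on that interval, not on NLR below 1. Do not make it a move-forward gate, because the study is unpowered. In a simulated case with specificity rising from 40% to 50% and equal sensitivity of 96-98%, its upper limit fell below 1 in only 6-7% of runs with 5 readers and 9-14% with 12.

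Cost: wider overall intervals, a few lines of SAP text and modest programming.
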